### 8.1 Length of Study

Participants will be recruited until 30 participants have been recruited, estimated time is approximately 3 months.

Participants will undergo a single RUAT ECHO, which takes approximately 30-60 minutes.

Participants will undergo a single safety follow-up contact up to 72 hours ~~18-24 hours~~ after the RUAT ECHO is performed, either in person if inpatient or by telephone call/telehealth if outpatient/discharged patient.

## 9 Participant Selection Criteria

To be eligible, participants must meet all of the inclusion criteria and none of the exclusion criteria.

### 9.1 Inclusion criteria:

- Male or female aged 18 years or older
- Inpatient or outpatient who has already received a routine (manual) echocardiogram that has been clinically reported.
- Is willing to participate.

	QMS Template	Doc ID: RMI-ROBOTECHO-CIP-002 Ver No: V2.0
	Clinical Investigation Protocol	

- Provides written informed consent.

## 9.2 Exclusion criteria:

- Is pregnant.
- Has poor patient mobility or is acutely symptomatic.

## 10 Study Procedures

Up to 30 participants will be required. Recruited participants will be RBWH Cardiology inpatients or outpatients who have already received a routine (manual) clinically reportable echocardiogram.

Study procedures and their timing are summarised in Figure 1 and the SoA (Section 4). Protocol waivers or exemptions are not allowed. Adherence to the study design requirements, including those specified in the SoA, is essential and required for study conduct.

All screening evaluations must be completed and reviewed to confirm that potential participants meet all eligibility criteria. The investigator will maintain a screening log to record details of all participants screened and to confirm eligibility or record reasons for screening failure, as applicable.

### 10.1 Administrative and Screening Procedures

#### 10.1.1 Screening and Recruitment

Prior to enrolment in the study, each participant will have already received a routine (manual) clinically reportable echocardiogram as an inpatient or outpatient.

Potential study participants will be selected based on inclusion and exclusion criteria, as above.

The potential study participant will be approached in person via a member of the study team (study coordinator or research staff as delegated by the principal investigator) while on the ward as an inpatient or in clinic as an outpatient. The study coordinator or research staff will provide details of the study (verbally and via the information sheet as part of the Participant Informed Consent Form 'PICF'), as outlined in Section 16.2.

At the time of informed consent potential study participants will be asked to disclose any bruising, soreness, or discomfort in the chest area that may impact safety outcomes that the RUAT study may have.

#### 10.1.2 Demographics

Participant demographics including age, sex, height and weight, will be collected at time of consent or RUAT echo.

Gender, height and weight information support the safe and effective conduct of an ultrasound, and or the interpretation of RUAT functionality. i.e., there are some technical challenges and differences in scanning female patients compared to male patients regarding chest shape, and patients with a larger body surface area can result in access issues or poor image quality.

[figure not shown]
### 10.2 RUAT ECHO Scanning

Only trained and competent sonographers (see Section 6) will undertake RUAT ECHO. Sonographers will perform RUAT ECHO according to their training and the RUAT ECHO User Instructions.

	QMS Template	Doc ID: RMI-ROBOTECHO-CIP-002 Ver No: V2.0
	Clinical Investigation Protocol	

The RUAT Echo will be performed with a cardiac sonographer in the examination room at a sonographer remote workstation but not at the bedside (*'Performing Sonographer'*). A second sonographer (*'Observing Sonographer'*) shall be at the bedside and supervise the procedure. The *Performing Sonographer* must not have been involved in the participant's initial clinical assessment.

The RUAT system is connected via ethernet cable to the sonographer remote workstation and a wired gaming controller is used to operate the robotic system.

**Figure 1: Scanning procedures**

	QMS Template	Doc ID: RMI-ROBOTECHO-CIP-002 Ver No: V2.0
	Clinical Investigation Protocol	

Cardiac sonographers will perform the RUAT Echo for up to 30 (total) recruited study participants. Although remotely performed in terms of the sonographer not holding the ultrasound probe in-hand (RUAT Echo exams), the *Performing Sonographer* will be physically co-located within the same room but not at the bedside of the study participant. This will provide patient and safety support for the procedure. The *Observing Sonographer* shall be at the bedside to supervise and verify that the RUAT performs as intended.

**Results of RUAT-performed echocardiograms will not be used for clinical treatment since treatment decisions would have already been made from the initial (manual) echocardiogram as the standard of care.**

The RUAT echocardiograms are only used to determine whether the images are of sufficient clinical quality to be reported on. In this regard 'clinical quality' refers to the images being classified as reportable by the sonographer.

At the end of the scan each study participant shall complete a RUAT experience survey.

## 10.2.1 Evaluation

### 10.2.1.1 Functional verification of RUAT ECHO

The *Observing Sonographer* will complete a functional verification checklist (see APPENDIX 1 - Functional Verification ) to verify that the RUAT echo was performed as intended (as described in the Instruction Manual).

### 10.2.1.2 Participant Experience Survey

Study participants' feedback on their experience from start to end of the RUAT echo will be collected via a feedback survey delivered to the participant by the *Observing Sonographer* or *health practitioner observer* at the completion of the RUAT echo. Data will be collected on the ability to interact with the *Performing Sonographer*, probe pressure and their perceptions on the movement of the robotic arm with invitation for open commentary and to express a preference for the manual versus robotic RUAT method (see

	QMS Template	Doc ID: RMI-ROBOTECHO-CIP-002 Ver No: V2.0
	Clinical Investigation Protocol	

APPENDIX 2 – Participant Experience Survey).

### 10.3 Adverse Events (AE), Adverse Device Events (ADE), Serious Adverse Events (SAE), Serious Adverse Device Event (SADE) and other Safety Reporting

The investigator and any qualified designees are responsible for detecting, documenting, and recording events that meet the definition of an AE/ADE or SAE and remain responsible for following up AEs that are serious, and considered related to the study intervention or study procedures.

To determine the safety of the RUAT echo, all AE/ADE/SAE/SADEs shall be recorded in the CRF and reported to the sponsor, ethics committee and TGA (if required) according to mandated timelines.

#### 10.3.1 Definitions

The definitions applied for reporting adverse incidents for medical devices are those defined in ISO 14155:2020 Edition 3, July 2020.

Adverse Event (AE): Any undesirable clinical occurrence in a subject whether it is considered device related or not, that includes a clinical sign, symptom, or condition and/or an observation of an unintended technical performance or performance outcome of the device.

Adverse Device Event (ADE): A clinical sign, symptom or condition that is causally related to the presence of the device, or the performance of the device system.

An adverse event or an adverse device effect may be mild, moderate, or severe.

Serious Adverse Event (SAE): Any adverse medical occurrence that:

- Led to a death.
- Led to a serious deterioration in health of a patient user or other. This would include:
  - A life-threatening illness or injury.
  - A permanent impairment of body function or permanent damage to a body structure.
  - A condition requiring hospitalisation or prolongation of hospitalisation.
  - A condition requiring unnecessary medical or surgical intervention.
- Might have led to death or serious deterioration in health had suitable action or intervention not taken place. This includes:
  - Malfunction of a device such that it needs to be modified or temporarily/permanently taken out of service.
  - A factor (a deterioration in characteristics or performance) found on examination of the device.

Serious Adverse Device Event (SADE): A device-related serious adverse event.

Unanticipated Device Related Adverse Event: Any undesirable clinical occurrence in a subject considered device-related and not listed in the device technical manuals/Investigator’s Brochure.

	QMS Template	Doc ID: RMI-ROBOTECHO-CIP-002 Ver No: V2.0
	Clinical Investigation Protocol	

### 10.3.2 Time Period and Frequency for Collecting AE, ADE, SAE and SADE Information

All AEs, ADEs, SAE and SADEs will be collected from the signing of the patient informed consent form (PICF) until 72 hours post RUAT Echo, i.e., end of the study.

### 10.3.3 Method of Detecting AEs and SAEs

Care will be taken not to introduce bias when detecting AEs, ADEs, SAEs and/or SADEs. Open-ended and nonleading verbal questioning of the participant is the preferred method to inquire about AE/ADE occurrences.

### 10.3.4 Classification System

Investigators will be asked to assess the potential relationship of the adverse event to the ROBOT ECHO and/or to the procedure. For this study, each AE/ADE will be classified as device- or procedure-related. The following definitions will be used:

- **Procedure-related:** An adverse event that occurs due to the system application procedure. Commonly experienced events from an Echocardiogram include potential bruising, discomfort, focused pressure from the probe, lubricating gel may feel cold.
- **Device Related:** An adverse event that results from the presence or performance of the device or any other component of the system, for example if the RUAT robotic arm pushes too hard on the patient and fractures a rib.
- **Unknown:** If the adverse event cannot be determined to have a causal relationship with either the device or procedure, it will be classified as unknown.

The severity or intensity of each AE/ADE will be classified as per the below definitions:

- **Mild:** Patient is aware of event or symptom, but event/symptom is easily tolerated.
- **Moderate:** Patient experiences sufficient discomfort to interfere with or reduce their usual level of activity.
- **Severe:** Significant impairment of functioning; patient is unable to carry out usual activities.

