
End-user (Sonographer & Patient) evaluation to understand if the selected technology is well-received
	
Most volunteers expressed some discomfort with the robot in the subcostal position. The discomfort was due to the continuous pressure applied on the belly and/or the feeling of being "imprisoned" under the robotic arm. One volunteer reported discomfort in the apical position due to the pressure on the ribs. In general, some volunteers expressed some stress/fear while being scanned, but none of the
	
Under review
	
There have been continuous positive responses received from both the sonographers and the patients with respect to the remote scan experiences over the evolution of the different device combinations used

	volunteers was contrary to the future use of a fully automated system for this type of scan. In general, the system was well received by the sonographers, who provided some suggestions to further improve the system		
--	--	--	--

Elements Analysed	Franka Panda Device (POC)	RUAT Device	Conclusions
Controllers	A touch haptic controller and a Logitech F710 controller were connected to the POC system. Sonographers were trained on the touch controller as it provides haptic feedback with 6 degrees of freedom (DOF). However, during the volunteer scanning, it was clear that the touch controller was considered challenging to operate. Moreover, movements requiring both translation and rotation pose a challenge with the touch controller. Controllers, which allow operation with both hands, might be easier to use and may have less of an impact on the sonographer	Logitech F310 Controller has been used. The controller allows the sonographer to manipulate the position of the probe, by sending commands to the robotic arm via the two NUCs (next unit of computing, i.e., minicomputer). Wired controllers were chosen due to having a more reliable connection and not being reliant on batteries.	Use of the Logitech Controller (Gamepad) in combination has resulted in better arm maneuverability and more effective scanning using the RUAT device

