#### 11.1.1 Decision Criteria

The primary objectives of the study are to:

- assess the **safety** of the RUAT echo.
- assess the **“useability” (functionality)** of using the RUAT echo as intended to obtain echocardiogram images of clinically suitable quality for reporting by a cardiac sonographer.

The **safety** of the RUAT Echo will be considered acceptable if there are no device related adverse effects.

RUAT Echo will be considered a **useable** method of performing echocardiograms if:

- Each functional verification criteria 1 through 11 (inclusive) performed “YES” at least 80% of the time an echocardiogram was performed by RUAT Echo, that is, pass functional verification (see APPENDIX 1 - Functional Verification ).
- At least 80% of echocardiograms performed by RUAT Echo are considered of an adequate quality to provide a diagnostic assessment, that is, pass functional verification item #12 (see APPENDIX 1 - Functional Verification ).
- At least 80% of participants report they are satisfied with undergoing RUAT Echo examination based on an average of the 4 subscales of the 10-point Likert scales from strongly disagree to strongly agree (see APPENDIX 2 – Participant Survey).

	QMS Template	Doc ID: RMI-ROBOTECHO-CIP-002 Ver No: V2.0
	Clinical Investigation Protocol	

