**Risk: Study Participant discomfort due to pressing of ultrasound probe on chest (Robot-assisted Ultrasound Examination)**

Mitigation: Participants will be informed of the potential for slight discomfort on the chest from pressing the ultrasound probe and that they can discontinue participation at any point if they find the pressure from the probe too uncomfortable to continue participation. The robot has an active pressure sensor with a limiter to prevent excess pressure being applied. The pressure limit is set to approximately 50% of the maximum pressure exerted by a human operator performing a standard ultrasound examination. A blue LED light on the sensor confirms pressure signals are actively being received and in the event of sensor failure, the pressure reading will drop to zero. Daily checks of the system include a manual test of the

	QMS Template	Doc ID: RMI-ROBOTECHO-CIP-002 Ver No: V2.0
	Clinical Investigation Protocol	

pressure sensor which requires applying gentle pressure to the probe holder and the sonographer is to confirm that the force indicator moves on the computer display for every force limit level (1-5).

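### The relatedness categories in Section 10.3.4 overlap for robot-applied probe pressure and no rule says which prevails, so the label chosen can decide the zero-event safety verdict in Section 11.1.1

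*Protocol*

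**What the plan says.** Section 11.1.1 sets a zero-event criterion for the first primary objective. The safety "of the RUAT Echo will be considered acceptable if there are no device related adverse effects".

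Section 10.3.4 supplies the labels. It first asks the investigator to assess the relationship to the robot 'and/or' the procedure. It then says: "For this study, each AE/ADE will be classified as device- or procedure-related". Three categories follow.

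- **Procedure-related**: arising from the procedure of applying the system. The examples are: "Commonly experienced events from an Echocardiogram include potential bruising, discomfort, focused pressure from the probe, lubricating gel may feel cold".
- **Device-related**: arising from the presence or performance of the device or any system component. The only example is a rib fracture caused by the arm pushing too hard.
- **Unknown**: no causal relationship with either can be determined.

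Section 10.3.1 defines an adverse device event as: "A clinical sign, symptom or condition that is causally related to the presence of the device, or the performance of the device system". It adds that such an event may be mild.

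Section 12 lists as its first participation risk "Study Participant discomfort due to pressing of ultrasound probe on chest", for the robot-assisted examination specifically. Section 10.3.5 leaves it to the investigator to decide whether a serious event was device-related.

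**The concern.** In a manual echo a person presses the probe. In a RUAT scan the robot does. A bruise or soreness from that pressure is a clinical sign related to the performance of the device system, so it is an adverse device event under 10.3.1 and device-related under 10.3.4. It is also one of the events that 10.3.4 names under procedure-related. Nothing says which category prevails or whether both may be ticked.

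Only device-related effects enter the safety rule, and one is enough to fail it. Two investigators who see the same participants and both follow the protocol could therefore reach opposite conclusions on the first primary objective. The terms do not help: Table 2 speaks of adverse device effects, 10.3.1 of adverse device events, and 11.1.1 of device-related adverse effects.

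A smaller gap lies alongside. Adverse events are collected from consent (10.3.2), so before the scan, in people who have recently had a manual echo and may already be sore. There is no 'not related' class for an event with another cause.

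**Working it through.** **1. The plan's own figure.** The only sample-size calculation (Section 11.6) concerns image quality. The Clopper-Pearson 95% interval for 24/30 = 80% comes out at 61.43% to 92.29%, a width of 30.9 points, which matches the stated 61.4% to 92.3%. No operating characteristic is given for the safety rule.

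**2. One event read through the text.** Take a mild chest bruise where the robot pressed the probe.

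| Text | Does the bruise fit? | Does it count in 11.1.1? |
|---|---|---|
| 10.3.1, adverse device event | Yes, through performance of the device system | Yes, if the rule means these events |
| 10.3.4, device-related | Yes, through performance of the device | Yes |
| 10.3.4, procedure-related | Yes, bruising is a named example | No, if this is the only label |
| 10.3.4, 'and/or' sentence | Both labels allowed | Not stated |

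**3. How far the label can move the verdict.** Inputs:
- n = 30 (Section 11.6).
- p, the proportion of participants with a robot-pressure event. This is an assumption, because the protocol gives no rate.
- f, the share of those events labelled procedure-related only. This is also an assumption.

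Participants are taken as independent, with no other device-related event occurring. Then

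P(pass) = (1 − p(1 − f))^30.

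At p = 10%: with f = 0, 0.90^30 = 4.2%; with f = 0.5, 0.95^30 = 21.5%; with f = 1, 1^30 = 100%.

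| Assumed p | All device-related (f = 0) | Half (f = 0.5) | None (f = 1) |
|---|---|---|---|
| 5% | 21.5% | 46.8% | 100% |
| 10% | 4.2% | 21.5% | 100% |
| 20% | 0.1% | 4.2% | 100% |

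**4. What a clean result would show.** With 0 of 30 events, the two-sided exact 95% upper limit is 1 − 0.025^(1/30) = 11.6%.

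**The case against.** The strongest reply is that the text already gives the right answer. The definitions of adverse device event (10.3.1) and device-related (10.3.4) agree, and both cover a bruise caused by the robot. The procedure-related list is introduced as what commonly follows any echocardiogram, so it can be read as background effects only. On that reading the investigator labels a robot-caused bruise device-related and nothing is lost. This stands as far as it goes: the definitions overlap and do not flatly contradict each other. But the protocol does not state that reading, and the list names the very effects that robot pressure would produce.

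Three stronger inferences are tempting, and the documents do not support them.

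- *That every event must carry exactly one label.* The 'or' sentence suggests it, but the 'and/or' sentence just before it allows both. The defect is the mismatch.
- *That the earlier experience shows the label will decide the result.* Table 1 does report: "Most volunteers expressed some discomfort with the robot in the subcostal position". That was a different robot arm, the discomfort was partly put down to feeling trapped under it, and no adverse event rate is given. The current device has a limiter set at about half of maximum manual pressure (Section 12), and the summary of the 78-participant study (Section 5.2) says examinations can be performed safely.
- *That robot pressure escapes scrutiny altogether.* All adverse events are recorded (10.3), graded for severity (10.3.4) and summarised (11.3.2.1). Reporting of serious events to the sponsor does not depend on the label (10.3.5). Item 3 of the participant survey asks about comfort with the robot's pressure and feeds the satisfaction criterion. None of this enters the safety verdict, but it limits the harm.

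Open assessment cannot be avoided in a single-group device study, and the co-investigator with a declared conflict is barred from recording or reviewing safety events (20.1). The missing 'not related' class alone does not change the verdict, since such events can be labelled unknown, which the rule does not count.

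**Conclusion.** The point holds as an overlap without a precedence rule. A foreseeable effect of the robot, named first in the protocol's risk list, fits both the category that fails the safety criterion and one that does not. The label can therefore decide the verdict on the first primary objective: at an assumed 10% event rate the chance of passing runs from 4.2% to 100% on labelling alone, with 21.5% if half the events are labelled device-related. The rates and shares are illustrative. The direction does not depend on them, because a zero-event rule turns on a single label.

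A reader might infer that the protocol removes the robot's main hazard from the safety assessment. It does not go that far. The events can drop out of the verdict but are not bound to, they remain in the adverse event data, and Section 12 does not rank its risks.

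This is not a detail to leave for the SAP. The protocol itself fixes both the categories and the rule, and attribution is made at the site when the event is recorded, so a later analysis document cannot cleanly repair it.

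**What to change.** Before the first scan, reconcile Sections 10.3.1, 10.3.4 and 11.1.1 and use one term for the event that counts.

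1. In 10.3.4, allow an event to be attributed to device and procedure together, and add a 'not related' class.
2. In 11.1.1, state that any event meeting the 10.3.1 definition of an adverse device event, alone or jointly with the procedure, enters the safety rule.
3. If expected mild contact effects are meant to be tolerated, write that into the rule itself, so that it does not depend on how they are labelled.
4. Beside the verdict, report procedure-related and unknown events with onset from the start of the scan, as a proportion of participants with an exact 95% interval.

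This does not require every contact symptom to be called device-related, or unknown events to count as failures. Separating ordinary echo effects from robot effects is a legitimate aim; it needs a stated boundary.

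The cost is rewording three sections and changing one CRF field. The real downside is that the zero-event rule may be harder to meet once jointly attributed events count, so the sponsor should decide on item 3 at the same time.

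### Section 10.3.4 gives no rule for a bruise or pressure discomfort that is both device- and procedure-related, and the zero-event safety verdict in Section 11.1.1 turns on which label is chosen

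*Protocol*

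**What the plan says.** Section 11.1.1 sets the primary safety criterion: safety "will be considered acceptable if there are no device related adverse effects". Events labelled procedure-related only, or unknown, do not enter it.

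Section 10.3.4 governs the label. It opens with "Investigators will be asked to assess the potential relationship of the adverse event to the ROBOT ECHO and/or to the procedure", which allows both relations at once. The next sentence reads "For this study, each AE/ADE will be classified as device- or procedure-related", which looks like one class per event. A third class, unknown, is for events that cannot be tied causally to either.

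The procedure-related class covers events due to the system application procedure and is illustrated by "Commonly experienced events from an Echocardiogram include potential bruising, discomfort, focused pressure from the probe, lubricating gel may feel cold". The device-related class is "An adverse event that results from the presence or performance of the device or any other component of the system"; its only example is a rib fractured by the arm pushing too hard. Section 10.3.1 defines an adverse device event as a sign, symptom or condition "causally related to the presence of the device, or the performance of the device system", with no severity threshold.

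**The concern.** In this study the robot arm holds the probe and presses it on the chest. A bruise or pressure pain that this causes fits the printed procedure-related examples, and it fits both causal definitions of a device event. The protocol does not say which label prevails or whether both may stand.

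These harms are foreseeable. The first risk listed in Section 12 is discomfort from the probe pressing on the chest during the robot-assisted examination. Table 1 reports that most proof-of-concept volunteers had some discomfort in the subcostal position, partly from continuous pressure, and that one had apical discomfort from pressure on the ribs. That was a different arm, and no numerical rate is given.

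At stake is the primary safety conclusion: two investigators who see the same events could reach opposite verdicts, each with support in the text. Expedited reporting by the sponsor in Section 10.3.6 also depends on the device-related label. A later analysis plan cannot cleanly repair this, because relatedness is an investigator's judgement made under the protocol's wording.

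**Working it through.** **Plan's own figure.** The protocol states no operating characteristic for the safety rule. Its only precision figure (Section 11.6) concerns image quality: the exact 95% interval for 24/30 is 61.43% to 92.29%, width 30.85%, which reproduces the stated 61.4% to 92.3% and 30.9%. It does not bear on safety.

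**Where one event lands.** Take a bruise caused by the robot-held probe.

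| Text | Where it places the bruise | Can it fail 11.1.1? |
|---|---|---|
| 10.3.4, procedure-related examples | Procedure-related | No |
| 10.3.4, device-related definition | Device-related | Yes |
| 10.3.1, adverse device event | Device event | Yes |
| 10.3.4, opening sentence (*and/or*) | Possibly both | Not stated |
| 10.3.4, next sentence (*or*) | One of the two, unspecified | Depends on the choice |

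**Inputs.**
- n = 30 (Section 11.6).
- Rule: pass only with zero device-related effects (Section 11.1.1).
- p = proportion of participants with a robot-contact bruise or discomfort. Not in the documents; varied.
- s = probability that such an event is labelled device-related. Not in the documents; varied.
- At most one such event per participant, independence between participants, and no other device event.

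**Formula.** A participant contributes a counted event with probability p × s, so P(pass) = (1 − p·s)^30.

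At p = 10%:
- s = 1: 0.90^30 = 4.2%
- s = 0.5: 0.95^30 = 21.5%
- s = 0.25: 0.975^30 = 46.8%
- s = 0: 1^30 = 100%

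| p | s = 0 | s = 0.25 | s = 0.5 | s = 1 |
|---|---|---|---|---|
| 5% | 100% | 68.6% | 46.8% | 21.5% |
| 10% | 100% | 46.8% | 21.5% | 4.2% |
| 20% | 100% | 21.5% | 4.2% | 0.12% |
| 30% | 100% | 9.6% | 0.8% | <0.01% |

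Within a row the harm is the same; only the label differs.

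**The case against.** The strongest reply is that the definitions are causal and already catch these events. Both the device-related definition and the adverse device event definition cover a bruise caused by the arm, however mild. The procedure-related list describes what is common in echocardiography generally and does not instruct anyone to label every bruise that way. The rib fracture is only an example, and as an injury from arm pressure it points excess robot pressure towards the device class. The *and/or* sentence already invites both judgements. All of this stands. A reader might infer that robot-caused bruising must fall in the uncounted class, so that the device would be declared safe whatever the rate. The text does not force that: the 100% column holds only if every such event is labelled procedure-related.

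The events are also not hidden. All adverse events are recorded (Section 10.3) and summarised (Section 11.3.2.1), serious ones go to the sponsor within 24 hours whatever their label (10.3.5), and survey item 3 asks about robot pressure and feeds a useability criterion. This stands too, but none of it enters the safety criterion. Nor can the planned summary by echocardiogram type substitute: collection starts at consent, after the manual echo, and no comparison is planned.

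Finally, the low pass probabilities at s = 1 come from a zero-event rule with 30 participants, not from Section 10.3.4. That is correct. What 10.3.4 contributes is the spread across each row.

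**Conclusion.** The point holds as a conflict within the protocol: overlapping relatedness classes, two sentences that disagree on whether both labels may apply, no tie-break, and a primary verdict that counts one class only. Foreseeable robot-contact harms can be placed where they cannot fail the safety rule.

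At an assumed 10% event rate in 30 participants, with no other device events, the chance of passing runs from 4.2% through 21.5% to 100% as the share labelled device-related goes from all through half to none. The rate and the share are assumptions, and the documents support no particular value of either. The conclusion that the label can reverse the verdict needs only that at least one such event occurs and no other device event does.

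**What to change.** Reconcile Sections 10.3.1, 10.3.4 and 11.1.1 before relatedness is first judged:

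1. In 10.3.4, replace the single classification with two separate causal judgements, relation to the device and relation to the procedure, so that an event can be both.
2. In 11.1.1, state that any event judged causally related to the robot's presence or performance counts, even if it is also procedure-related or common in manual echo.
3. Have the device judgement take account of bruising or soreness already documented at screening (Sections 4 and 10.1.1). Do not assign relatedness by anatomical site alone: every participant has had a manual echo, so a site rule could count carry-over from that scan and would replace causation with location.
4. Report the device-related, procedure-related and both counts side by side.
5. If the sponsor wishes mild, expected discomfort not to fail the device, it should state that tolerance openly in 11.1.1 and not leave it to the label.

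The cost is wording in these sections and one extra field on the case report form. The downside is that the zero-event criterion becomes harder to meet.
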